**Table 2** **Visit Window of Vital Signsb)**

Analysis time point	Visit Window	
Screening	Within 21 days prior to IMP administration	
Day -1	Within Day -1	
Day 1	1 hr	0.75 hr to <1.25 hr
	1.5 hr	1.25 hr to <1.75 hr
	2 hr	1.75 hr to <2.25 hr
	2.5 hr	2.25 hr to <2.75 hr
	3 hr	2.75 hr to <3.25 hr
	3.5 hr	3.25 hr to <3.75 hr
	4 hr	3.75 hr to <4.5 hr
	5 hr	4.5 hr to <5.5 hr
	6 hr	5.5 hr to <6.5 hr
	7 hr	6.5 hr to <7.5 hr
	8 hr	7.5 hr to <8.5 hr
	9 hr	8.5 hr to <9.5 hr
Day 2	10 hr	9.5 hr to <11 hr
	12 hr	11 hr to <13 hr
Day 2	Within Day 2	
Day 3	Within Day 3	
Day 5	Within Day 5	
Day 8	Within Day 8	
Follow-up Week 2	Day 12 to Day 16	
Follow-up Week 4	Day 26 to Day 30	
Follow-up Week 6	Day 40 to Day 44	
Study Completion Visit (Week 14) / Withdrawal (WD)	Day 96 to Day 100 or when the subject is withdrawn	

b) Body weight and height will be collected at Screening, and body weight at Study Day -1 and Study Completion Visit (Week 14)/ Withdrawal (WD).

**Table 3** **Visit window of the other items**

Analysis time point	Visit Window	Laboratory a)	ADA	Physical Examination c)	12-lead ECG	Pregnancy Test d)
Screening	Within 21 days prior to IMP administration	X		X	X	
Day -1	Within Day -1	X		X		
Day 1	Preinfusion	Before IMP administration within Day 1		X	X	

Analysis time point		Visit Window	Laboratory a)	ADA	Physical Examination c)	12-lead ECG	Pregnancy Test d)
1 hr 2 hr 4 hr 8 hr 10 hr 12 hr	1 hr	0.75 hr to <1.25 hr					
	2 hr	1.75 hr to <2.25 hr					
	4 hr	3.5 hr to <4.5 hr	X			X	
	8 hr	7.5 hr to <8.5 hr					
	10 hr	9 hr to <11 hr					
	12 hr	11 hr to 13 hr					
Day 2	Within Day 2	X					
Day 3	Within Day 3	X					
Day 5	Within Day 5	X					
Day 8	Within Day 8	X					
Follow-up Week 2	Day 12 to Day 16	X					
Follow-up Week 4	Day 26 to Day 30	X					X
Follow-up Week 6	Day 40 to Day 44	X					
Follow-up Week 8	Day 54 to Day 58						X
Follow-up Week 10	Day 68 to Day 72	X b)					
Follow-up Week 12	Day 82 to Day 86						X
Study Completion Visit (Week 14) / Withdrawal (WD)	Day 96 to Day 100 or when the subject is withdrawn	X	X	X	X	X	

a) Laboratory includes hematology, chemistry, and urine and hematology measurements, taken under fasting condition except from screening.

b) Only hematology and chemistry.

c) A full physical examination will be performed at screening and at Week 4 visit. At all other visits brief physical examinations will be performed, only if indicated.

d) Urine pregnancy test is to be performed with a dipstick at week 4, 8, 12 and study completion.

#### 8.4.4 Baseline

Baseline is defined as the last non-missing value taken before the study drug administration.

#### 8.5 Rounding digits

##### 8.5.1 Displaying of Descriptive Statistics

- Mean, Median and Geometric Mean

Round to one more significant digit than what was used to collect the variable.

- Standard Deviation

Round to two more significant digit than what was used to collect the variable.

- Minimum and Maximum

Round to the same number of significant digits used to collect the variable.

## **8.5.2 Rounding Digits for Percentages (including CV%)**

Round to the nearest tenths (0.1).

## **8.6 Handling of Missing Data and Outliers**

### **8.6.1 Handling the Date of Adverse Events**

#### **8.6.1.1 TEAE**

In the case of partially or completely missing AE start date/time, the AE will be considered treatment emergent, unless the available date/time information clearly indicates that the AE started prior to start of the IMP infusion as follows:

- If the start time is missing, but start date is before start date of IMP infusion.
- If the day of the AE is missing, but the year/month are before the year/month of the start of IMP infusion.
- If the day and month of the AE are missing, but the year is before the year of the start of IMP infusion.
- If the stop date of the AE is before the start date of the IMP infusion.

#### **8.6.1.2 IRR**

If the onset time of the AE or the start time of the infusion is missing, then an AE with an onset date equal to the infusion date or infusion date + 1 will be considered for the assessment of Infusion Related Reactions (IRRs), unless the available information clearly indicates that the AE was not treatment-emergent.

If the onset date/time of the AE is completely missing, the AE will be considered as IRR.

#### **8.6.1.3 Severity and Relationship**

The relationship to study drug and severity of AEs are assessed by the Investigator and recorded in eCRF.

If the relationship of an AE is missing, it will be assumed as related to study drug for presentation in summary tables, unless the AE is not treatment-emergent.

If severity of an AE is missing, it will be considered as severe for presentation in summary tables.

## **8.7 Multicenter Studies**

Not applicable. This is a single center study.

## **8.8 Multiple Comparisons and Multiplicity**

As no formal hypothesis testing will be performed, adjustment for multiple comparisons is not applicable.

# **9 Subject Disposition**

## **9.1 Subject Disposition**

Population:      Consented Subjects

Group:            Emapalumab, Placebo

Contents:

- Calculate the number of subjects by groups for the following items:
  - Informed consent
  - Screened
  - Screen failure
    - Primary reason for screen failure
      - Did not meet all eligibility criteria
      - The trial was prematurely terminated
      - Subjects wishes to withdraw from the trial
      - Investigator's decision
      - Withdrawn due to an adverse event
      - Reserved subject
      - Death
      - Lost to follow-up
      - Other
    - Randomized subject
    - Randomized, but not treated
    - Receiving IMP
    - Completed study
    - Discontinued study
      - Primary reason for discontinuation
        - The trial was prematurely terminated
        - Subjects wishes to withdraw from the trial

- Investigator's decision
- Withdrawn due to an adverse event
- Reserved subject
- Death
- Lost to follow-up
- Other
- Denominator for Screened, Screen Failure will be the Consented Subjects.
- Denominator for Primary reason for screen failure will be the number of Screen failure.
- Denominator for Randomized, but not treated, Treated investigational product, Completed study and Discontinued study will be the number of Randomized subjects in each group.
- Denominator for Primary reason for discontinuation will be the number of Discontinued study in each group.

## **9.2 Protocol Deviations**

Population: Randomized Subjects

Group: Emapalumab, Placebo

Contents:

- Calculate the number of subjects and the percentages of those with and without deviations from the protocol with their deviation contents by groups (Refer to protocol section 9.4 Protocol Deviations).
- Denominator to calculate the percentage will be the number of subjects from the population in each group.
- Subjects with more than one protocol deviations will be counted once for each category.
- Both major and minor protocol deviation will be presented.

## **9.3 Analysis Dataset**

Population: Randomized Subjects

Group: Emapalumab, Placebo

Contents:

- Calculate the number and percentages of subjects by groups in the following population:

- Randomized Subjects
- Safety Analysis population (Qualified/Unqualified)
- PK/PD population (Qualified/Unqualified)
- Calculate the number of unqualified subjects by reasons in PK/PD and Safety Analysis population.

## 10 Demographics and baseline characteristics

### 10.1 Demographics and Other Baseline Characteristics

Population: Safety Analysis population, PK/PD Analysis population

Group: Emapalumab, Placebo

Contents:

- For categorical data and ordinal data, calculate the number of subjects and percentages.
- For continuous data, calculate the descriptive statistics.

Definitions:

- BMI  
BMI at screening will be calculated using the following formula:

$$\text{BMI} = \frac{\text{Weight [kg]}}{(\text{Height [m]})^2}$$

- Unknown and Missing values  
If unknown or missing values are observed, add “Unknown” category and only calculate the number of subjects. Remove “Unknown” category from the denominator for percentages.
- Race is only displayed in the listing.

[Background Factors]

Classification [Unit]	Category
Age [Year]	<30, 30≤ <40, 40≤
	Descriptive statistics
Sex	Male, Female
Height [cm]	Descriptive statistics
Weight [kg]	Descriptive statistics
BMI [kg/m  ]	Descriptive statistics

### 10.2 Medical History

Population: Safety Analysis population

Group: Emapalumab, Placebo

Contents: 

- Calculate the number of subjects and percentages for each PT by groups.

Definitions: 

- Denominator to calculate the percentage: The number of subjects from the population in each group.
- Subjects who have same PTs are counted only once for each PT.

## 11 Prior and Concomitant Medication

Population: Safety Analysis population

Group: Emapalumab, Placebo

Contents: 

- Calculate the number of subjects and percentages for each prior/concomitant medications by groups, using the entered codes.
- Subjects using at least one prior/concomitant medications with each effect will be counted.

Definitions: 

- Prior Medications: Any medication which ended before the day of IMP administration.
- Concomitant Medications: Any medication which started on or after the day of IMP administration or any medication taken prior to the day of IMP administration and continued after IMP administration.
- Denominator to calculate the percentage: The number of subjects from the population in each group.
- Subjects who take multiple drugs with the same generic names are counted only once for each drug. Subjects who take multiple drugs in the same drug effects are counted only once at each drug effects.

## 12 Treatment compliance

Not applicable.

## 13 Efficacy analyses

Efficacy analyses will not be conducted.

## **14 Pharmacokinetic and pharmacodynamic assessment**

### **14.1 Pharmacokinetic assessment**

PK parameters will be calculated using the actual time and actual dose of study drug of collected samples. Sample collected before administration will be analyzed as time point 0 hours. Linear Trapezoidal Linear Interpolation will be used to calculate AUC and AUMC, by using actual elapsed time values. Data points BLOQ in the end of the serum concentration time curve will be omitted from estimation of AUC and AUMC using Phoenix WinNonlin.

The list of pharmacokinetic parameters derived in this study are presented in Table 4.

**Table 4 List of pharmacokinetic parameters**

Parameter	Description	Unit	Display Digits
$C_{\max}$	Maximum observed serum concentration	ug/L	3 significant figures
$t_{\max}$	Time to $C_{\max}$	h	2 decimal places
CEOI	Observed concentration at end of infusion	ug/L	3 significant figures
$AUC_{\text{last}}$	Area under the serum concentration-time curve from time 0 to the time corresponding to the last quantifiable serum concentration $AUC = \int_0^t C$	ug*h/L	3 significant figures
$AUC_{\text{inf\_calc}}$	Area under the serum concentration-time curve extrapolated to infinity, calculated using the formula: $AUC_{\text{inf\_calc}} = AUC_{\text{last}} + Ct/\lambda z$ , where Ct is the predicted concentration at tlast and $\lambda z$ is the apparent terminal phase rate constant. Values of $AUC_{\text{inf\_calc}}$ will only be deemed reliable if $\lambda z$ is reliably estimated and if % AUCextr is less than 20%.	ug*h/L	3 significant figures
%AUCextr	Percentage of extrapolated AUC from T last to infinity time $= \frac{AUC_{\text{INF\_calc}} - AUC_{\text{last}}}{AUC_{\text{INF\_calc}}} \times 100$	%	1 decimal place
$AUMC_{\text{last}}$	Area under the first moment curve from the time of dosing to the last measurable concentration. $AUMC_{\text{last}} = \sum_{i=1}^{\text{last}} (t_{(i+1)} - t_i) \cdot \frac{t_i \cdot C_i + t_{(i+1)} \cdot C_{(i+1)}}{2}$ i=timepoint(1,2,⋯, last)	ug*h*h/L	3 significant figures
$AUMC_{\text{inf\_calc}}$	Area under the first moment curve (AUMC) extrapolated to infinity, based in the last predicted concentration. $= AUMC_{\text{last}} + \frac{t_{\text{last}} - Clast_{\text{pred}}}{\lambda z} + \frac{Clast_{\text{pred}}}{\lambda z^2}$	ug*h*h /L	3 significant figures
$\lambda z$	Terminal rate constant The first-order rate constant for the terminal phase (log-linear) part of the curve. Estimated by linear regression of time-logarithmic concentration. If the number of measurement results with a value greater than 0 and less than 3 points measured after $C_{\max}$ is not calculated by WinNonlin. The associated $R^2$ of the estimate is required to be $>0.8$ in order to be reliably estimated.	1/h	2 decimal places
$t_{1/2}$	Terminal half-life, where $t_{1/2} = \ln(2)/\lambda z$	h	3 significant figures
CL	Total systemic clearance $= \frac{\text{Dose}}{AUC_{\text{INF\_calc}}}$	L/h	3 significant figures

	CL is calculated using dose level (mg/kg) and actual dose (mg).		
V ss	
Steady state volume of distribution
 
Calculate from the following formula in subjects whose <math>\lambda_z</math> can be calculated.
 $V_{ss} = CL \times MRT_{inf}$ 
Vss is calculated using dose level (mg/kg) and actual dose (mg).
	L	3 significant figures
MRT last	
Average residence time from the start of infusion to the final blood collection time
 $= \frac{AUMC_{last}}{AUC_{last}} - \frac{TI}{2}$ 
TI :Duration of infusion
	h	3 significant figures
MRT inf	
Average residence time from start of infusion to infinite time
 $= \frac{AUMC_{inf\_calc}}{AUC_{INF\_calc}} - \frac{TI}{2}$ 
TI :Duration of infusion
	h	3 significant figures

Subjects will be excluded from the PK analysis if their data do not allow for accurate assessment of the PK (e.g. incomplete administration of the study drug; subject vomited after receiving study drug; missing information of dosing and sampling times; concentration data not sufficient for PK parameter calculation).Following rules will be applied for descriptive statistics.

- Lower Limit of Quantification (LLOQ) will be substituted with 0.
- The number of subject displayed as "N" on summary tables will be the number of subject whose serum concentrations are measured (include LLOQ) or PK parameters are calculated.
- When the time of blood collection is outside the time windows, the relevant serum concentration will be listed but excluded from the calculation of summary statistics.

**Table 5** List of compound and lower limit of quantification

Compound	Unit	Lower Limit of Quantification	Rounding Digit
Emapalumab	ug/L	62.5 ug/L	0.01

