4.1.2.3 Clinical Data

Since the start of the clinical development program for emapalumab, more than 100 patients have received emapalumab in clinical trials and through compassionate use. Furthermore, more than 70 patients have been treated to date in the US following FDA approval, and post-marketing surveillance has not revealed any additional safety concerns with the use of emapalumab.

Emapalumab has been granted Orphan Drug Designation in the United States (US) on 26 March 2010 and in Europe (EU) on 09 June 2010. Emapalumab has obtained Breakthrough designation in US on 11 March 2016 and PRIME designation in EU on 26 May 2016.

On 20 November 2018 the FDA approved emapalumab for the treatment of adult and pediatric (newborn and older) patients with pHLH with refractory, recurrent or progressive disease or intolerance with conventional HLH therapy.

The FDA approval was based on data from study NI-0501-03, interim data from the pivotal study NI-0501-04 and interim data from the long-term follow-up study NI-0501-05.

Study NI-0501-03 was a phase 1 randomized double-blinded placebo-controlled single ascending dose study, in 20 healthy adult volunteers investigating the safety, tolerability and pharmacokinetic (PK) profiles of single intravenous (IV) administrations of emapalumab took place between September 2011 and January 2013. During this study, 6 subjects received placebo, while 3, 3, 4, and 4 subjects (in total 14 subjects) received emapalumab doses of 0.01, 0.1, 1, and 3 mg/kg, respectively.

Emapalumab PK data from healthy volunteers were evaluated using a population modeling approach. The PK of emapalumab was best described by a two-compartment model (NI-0501-03 - Modelling and Simulation support to NI-0501 PK analysis of study NI-0501-03). In healthy volunteers, emapalumab has the typical PK profile expected for a mAb, with low central and peripheral volumes of distribution (3.02 L and 2.83 L), slow clearance (0.007 L/h) and long distribution and terminal half-lives (1.55 and 25.4 days).

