6.6.3 Methods of assigning subjects to treatment groups

A single intravenous dose of 1 mg/kg is considered relevant for this Phase 1 study in Japanese healthy subject to bridge to the global Phase 1 study NI-0501-03 where single dose administration of 0.01, 0.1, 1 and 3 mg/kg were administered.

Because the PK of emapalumab in healthy adults is linear, one dose level is sufficient for a comparison between Japanese and non-Japanese. Also, a single dose is sufficient to compare PK between Japanese and non-Japanese, since the PK of emapalumab does not show any time-dependency upon repeated-dose since administration.

The global Phase 1 study (NI-0501-03) in 20 healthy adult volunteers investigated the safety, tolerability and PK profiles of single IV administrations of emapalumab. During this study 6 subjects received placebo, while 3, 3, 4, and 4 subjects (in total 14 subjects) received emapalumab doses of 0.01, 0.1, 1, and 3 mg/kg, respectively. All IMP infusions were uneventful, and most AEs were singular occurrences and no trend in relation to increasing emapalumab dosage was observed.

The PK analysis of emapalumab in the NI-0501-03 study revealed the expected profile for an IgG1 with a long half-life (around 22 days), a slow clearance (≤ 0.1 mL/kg/hr) and a low volume of distribution (<65 mL/kg on average). The serum concentrations following 1 mg/kg were

pharmacologically relevant since Cmax (32 200 ng/mL) was approximately 50 times the IC50 (603 ng/mL) for significant neutralization of IFN γ .

Considering the scaling factor from the Non-human primate to human (x0.32). 30 mg/kg (NO AEL) which was very well tolerated in monkeys, with no adverse clinical signs or organ toxicity reported, correspond to a HED of 10 mg/kg, therefore the 30 mg/kg in monkey is 10-fold higher than the starting dose in human of 1 mg/kg

Taken these aspects into account, a single intravenous dose of 1 mg/kg emapalumab has been selected for the Phase 2-3 study in pHLH thus this dose is selected also for this study in Japanese healthy subjects.

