6.7.1.5 Study completion visit (W14) or withdrawal

At the last visit (Study completion visit) the subjects will undergo assessment and procedures according to the schedule of events (Table 4). The time window for this visit is \pm 2 days.

The same assessment and procedures should be conducted at a withdrawal visit for any subject who withdraws prematurely or is withdrawn by the investigator. The withdrawal visit should be scheduled within 30 days of termination.

Subjects withdrawn due to a SAE should be followed-up until resolution of the event or until the outcome is known and stable.

In order to measure the emapalumab serum levels during at least 3 times the terminal half-life (a total of approximately 3 months) PK samples will be taken up to week 14.

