## **4 Study methods**

### **4.1 Overall study design and plan**

[figure not shown]
This is a randomized, placebo-controlled and double-blinded study to evaluate the PK, PD and safety of a single i.v. dose (1 mg/kg) of emapalumab in adult healthy Japanese subjects, performed in Japan. 8 subjects will be randomized to receive either emapalumab or matching placebo in a 3:1 ratio (emapalumab: placebo). The investigator, study subjects and sponsor will be blinded to treatment allocation (placebo and active) to avoid reporting, assessment and allocation biases. It is considered sufficient with 6 subjects randomized to emapalumab, considering the inter-subject variability in the PK results in the NI-0501-03 study.

Figure 1 shows the study design.

Study subjects will be screened within 21 days prior to administration of investigational medicinal products (IMP). An additional visit will take place within 96 hours prior to IMP infusion for collection of a PCR test for SARS-CoV-2. Eligible subjects will be admitted to the clinical unit the day before drug administration (Study Day -1). On Day 1 of the admission

period subjects will receive a single dose of emapalumab (1 mg/kg) or placebo administered as a 1-hour infusion. Subjects will be discharged from the unit on Day 8. PK samples will be collected up to Week 14 in order to measure the emapalumab serum levels during at least 3 times the terminal half-life (a total of approximately 3 months). All subjects will be followed-up on regular visits for a minimum of 14 weeks after a single infusion of emapalumab. In addition, any subject with ongoing SAEs at study completion will be followed-up until resolution of the event or until the outcome is known and stable.

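### SAP Table 4 sets no minimum time span for lambda_z, so a half-life fitted to Weeks 10-14 alone (about 1.1 half-lives) counts as reliable

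*SAP*

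**What the plan says.** The lambda_z row of SAP Table 4 describes a log-linear regression on the terminal phase and adds two conditions. One is a count: "If the number of measurement results with a value greater than 0 and less than 3 points measured after" Cmax, which I read as no calculation with fewer than three quantifiable points. The other is fit: R-squared "of the estimate is required to be $>0.8$ in order to be reliably estimated".

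Neither document gives a rule for choosing the points, a minimum span, or an adjusted R-squared. The 20% limit on extrapolated area in the same table applies to AUCinf only. SAP 14.1.3 has the points used for half-life shown on the individual profiles.

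SAP 4.1 explains why sampling runs to Week 14: "in order to measure the emapalumab serum levels during at least 3 times the terminal half-life (a total of approximately 3 months". Protocol 6.1 and 6.7.1.5 give the same reason. SAP Table 1 schedules PK samples at Weeks 2, 4, 6, 8, 10, 12 and 14.

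**The concern.** Lambda_z and t1/2 are named primary PK endpoints, and Protocol 4.2 says the results will be compared with the non-Japanese study NI-0501-03. The schedule pays for a long terminal phase, but the reliability rule does not require the slope to use it. A slope over about one half-life can be labelled reliable. Its fitting noise would then enter the summary of six treated subjects as if it were variability between subjects.

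**Working it through.** **Inputs.**
- From Protocol 4.1.2.3: "long distribution and terminal half-lives (1.55 and 25.4 days" and "low central and peripheral volumes of distribution (3.02 L and 2.83 L), slow clearance (0.007 L/h".
- From Protocol 6.6.3, an alternative half-life: "expected profile for an IgG1 with a long half-life (around 22 days".
- From SAP Table 1: nominal Days 14, 28, 42, 56, 70, 84 and 98, each ±2 days.
- From SAP Table 5: LLOQ 62.5 ug/L.
- Assumed, not in the documents: constant proportional residual error of 5-20%, and points chosen by best adjusted R-squared.

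**1. The plan's own figure.** 98/25.4 = 3.9 half-lives and 98/22 = 4.5. The claim of at least 3 is reproduced.

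**2. The shortest late fit the rule admits.** Weeks 10-14: 98 - 70 = 28 days. 28/25.4 = 1.10 half-lives (28/22 = 1.27). With visit windows the span is 24-32 days, or 0.94-1.26 half-lives at 25.4 days. The two-compartment model, with 60 kg assumed, predicts about 1346, 919 and 627 ug/L at these visits, all well above the LLOQ, so the set is available in practice.

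**3. What R-squared = 0.8 means with three points.** t = sqrt(R²(n-2)/(1-R²)) = sqrt(0.8/0.2) = 2.0 on 1 df, so p = 0.295. Adjusted R-squared is 1 - 0.2 × 2/1 = 0.60. The 95% half-width of the slope is 12.71/2.0 = 6.35 times the slope, so the interval includes zero and t1/2 has no finite upper limit. This step needs no assumed error.

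**4. Precision of the two windows.** SE(lambda_z) = residual SD / sqrt(Sxx). For Weeks 10-14, sqrt(2 × 14²) = 19.8 days; for Weeks 2-14, sqrt(28 × 14²) = 74.1 days. The short window therefore has 74.1/19.8 = 3.7 times the standard error, whatever the size of the residual error. With lambda_z = ln 2/25.4 = 0.0273 per day and 10% error: 0.1/19.8/0.0273 = 18.5%, against 0.1/74.1/0.0273 = 4.9%.

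**5. Simulation of the rule as a whole.** SD of log t1/2:

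| Assumed residual error | Points by best adjusted R-squared | Weeks 2-14 always (formula in step 4) | Weeks 10-14 fits with R-squared > 0.8 |
|---|---|---|---|
| 5% | 6.0% | 2.5% | 100% |
| 10% | 11.7% | 4.9% | 98% |
| 15% | 16.9% | 7.4% | 89% |
| 20% | 21.1% | 9.9% | 78% |

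Under that selection about 20% of fits use only three points, and R-squared > 0.8 rejects none of the selected fits. Half-life is wrong by more than 20% in about 1, 9, 15 and 20% of subjects, against about 0, 0, 1 and 5% with Weeks 2-14. Adding only a 2-half-life span condition to the same selection brings the SD down to about 3% at 5% error and about 13% at 20%.

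**6. Effect on the group summary.** If the true between-subject CV of t1/2 is 20% (assumed), the interval for its mean widens by about sqrt(20² + 6.0²)/sqrt(20² + 2.5²) = 1.04 at 5% error, sqrt(20² + 11.7²)/sqrt(20² + 4.9²) = 1.13 at 10%, and sqrt(20² + 21.1²)/sqrt(20² + 9.9²) = 1.30 at 20%.

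**7. Other parameters.** At Week 14 the model leaves about 6% of AUCinf to extrapolation. At 10% error the SD is 3.3% against 3.2% for CL, and 5.9% against 5.5% for Vss.

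**The case against.** A reader might infer that the rule defeats the sampling over three half-lives. The documents do not support that. The horizon is given as the reason for measuring serum levels to Week 14, not as a condition on the slope. The late samples still serve AUClast, the extrapolated fraction and the profile, and the rule permits a 28-day slope without requiring one.

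A reader might also infer serious contamination by the distribution phase, or damage to every parameter derived from lambda_z. Neither holds. Table 4 confines the fit to the terminal phase in principle. In the simulation the median t1/2 at 10% error is 24.9 days against a true 25.4, and at 5% error only about 4% of fits reach back to Day 5 or earlier. AUCinf, CL and Vss hardly move (step 7).

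The plan has safeguards: SAP 14.1.3 shows the points used, and SAP 14.1 excludes subjects whose data do not allow accurate PK assessment. These disclose a poor fit or remove a subject with inadequate data. They do not say which points to fit, or stop a short fit in a subject with complete data.

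The size rests on two assumptions outside the documents. Most of the loss comes from the assumed selection method, under which passing R-squared is nearly automatic, and at 5% error the harm is modest. That stands. Steps 2 to 4 do not depend on how points are selected, and steps 2 and 3 need no assumed error. The study is descriptive, so no test is at risk.

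**Conclusion.** The point holds as a weakness in a stated reliability rule, and it should be corrected. Three points with R-squared above 0.8 is too weak a standard for t1/2, because it accepts 28 days (about 1.1 half-lives) and does not secure for t1/2 the benefit of the long sampling. Under the two stated assumptions the SD of log t1/2 is about 6-21%, at least double the 2-10% from Weeks 2-14. The consequence is confined essentially to lambda_z and t1/2.

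**What to change.** In the lambda_z row of SAP Table 4:
- Make the default fit all quantifiable samples from Week 2 to the last one: 7 points, 84 days, 84/25.4 = 3.3 half-lives. Week 2 is 14/1.55 = about nine distribution half-lives after dosing.
- Allow a departure only with a documented reason drawn from the subject's own profile, since the study is meant to check whether the earlier PK carries over.
- Call lambda_z and t1/2 reliable only if the fitted points also span at least 2 estimated half-lives. Otherwise list and flag t1/2 and leave it out of the summary statistics.
- Report span and number of points per subject.

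The value 2 is a judgement, but the schedule supports it: Weeks 6-14 already give 56/25.4 = 2.2 half-lives.

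The cost is wording, with no new samples; SAP 5.2 allows revision before database lock. There are three downsides. A subject who withdraws at Week 8 has Weeks 2-8 = 42 days, 42/25.4 = 1.65 half-lives, and would have t1/2 flagged. So would a subject with complete data and an estimated half-life above 84/2 = 42 days. An atypical late decline would need a documented override.

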#### **14.1.4      Pharmacokinetic Parameters**

Population: PK/PD population

Group: Emapalumab

Contents: • Calculate the descriptive statistics of pharmacokinetic parameters defined in Table 4 in Section 14.1 Pharmacokinetic assessment by groups.

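### SAP Table 4 displays λz, a primary PK parameter, in 1/h to 2 decimal places, so individual values are expected to print as 0.00

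*SAP*

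**What the plan says.** Protocol 5.1.1 and SAP 3.3.1 both name λz among the primary PK parameters. SAP Table 4 defines it as "The first-order rate constant for the terminal phase (log-linear) part of the curve". The row closes with the R² criterion, then the unit and display-digit cells: "in order to be reliably estimated. 1/h 2 decimal places". Of the 14 rows in Table 4, 11 use 3 significant figures. The exceptions are tmax, %AUCextr and λz.

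SAP 14.1.4 carries these parameters into the summary table ("Calculate the descriptive statistics of pharmacokinetic parameters defined in Table 4 in Section 14.1"), and SAP 16 includes a listing of individual PK parameters.

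SAP 8.5.1 gives general rounding rules. For the mean, median and geometric mean: "Round to one more significant digit than what was used to collect the variable". For the minimum and maximum: "Round to the same number of significant digits used to collect the variable". The standard deviation gets two extra digits.

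The protocol gives two half-lives from the earlier healthy-volunteer study. Section 4.1.2.3 reports "long distribution and terminal half-lives (1.55 and 25.4 days" from the population model, and section 6.6.3 reports "a long half-life (around 22 days". Section 6.6.3 also states, for 1 mg/kg, that "Cmax (32 200 ng/mL) was approximately 50 times the IC50 (603 ng/mL".

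For the log-transformed concentration plots, SAP 14.1.2 and 14.1.3 list scale values from 10^-1 to 10^4, with concentration in ug/L.

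**The concern.** A fixed number of decimals suits a quantity of known, moderate size. For an antibody with a half-life of several weeks, λz expressed per hour is about one thousandth, so its leading digit lies beyond the second decimal. Following Table 4 exactly would fill the individual λz values with 0.00, and part of a primary-endpoint display would tell the reader nothing.

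The setting also departs from the table's own pattern. t½ is defined from λz and contains the same information, yet it is shown to 3 significant figures. The other two exceptions, tmax in hours and %AUCextr in percent, have formats that suit their size.

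The log-scale list raises a smaller question of the same kind: whether a display setting was checked against the values expected at this dose.

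**Working it through.** **Inputs.** Half-lives of 22 and 25.4 days (Protocol 6.6.3 and 4.1.2.3); t½ = ln(2)/λz (SAP Table 4); display at 2 decimals in 1/h (SAP Table 4); Cmax 32,200 ng/mL and IC50 603 ng/mL (Protocol 6.6.3).

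**1. Reproduce the protocol's figures.**
- Cmax/IC50 = 32,200/603 = 53.4, which agrees with the stated factor of about 50.
- Terminal half-life: take CL 0.007 L/h, V1 3.02 L and V2 2.83 L from Protocol 4.1.2.3. The inter-compartmental flow is not given; a value of 0.0255 L/h reproduces the stated distribution half-life of 1.55 days. Then k10 = 0.007/3.02 = 0.00232, k12 = 0.0255/3.02 = 0.00844 and k21 = 0.0255/2.83 = 0.00901 per hour. The smaller root of x² − (k10 + k12 + k21)x + k10·k21 = 0 is 0.00112 per hour, a half-life of 25.8 days. This is within 2% of the stated 25.4.

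**2. Expected λz.**
- 22 days: ln(2)/(22 × 24) = 0.6931/528 = 0.00131 per hour.
- 25.4 days: ln(2)/(25.4 × 24) = 0.6931/609.6 = 0.00114 per hour.

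At 2 decimals both are 0.00.

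**3. When the display would change.** Printing 0.01 needs λz of at least 0.005 per hour, so t½ ≤ ln(2)/0.005 = 138.6 h = 5.8 days. The protocol's half-lives are 22/5.78 = 3.8 and 25.4/5.78 = 4.4 times that.

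**4. Between-subject variation.** Protocol 8.1 and SAP 6 put the inter-subject CV within 30% for parameters such as Cmax and AUC. Applying 30% to λz is an assumption. Two SDs above the larger expected value is 0.00131 × (1 + 2 × 0.30) = 0.0021 per hour. Doubling the CV to 60% gives 0.00131 × 2.2 = 0.0029. Both are below 0.005, so every individual value is still expected to print 0.00.

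**5. Summary statistics.** SAP 8.5.1 is worded for collected variables and speaks of significant digits, whereas λz is derived and its format is set in decimals. If the rule is nevertheless applied as extra decimals to the Table 4 format, the mean, median and geometric mean have 3 decimals and print 0.001 at either half-life. The SD has 4 decimals, and the minimum and maximum stay at 0.00.

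**6. What 3 significant figures would show.** 0.00131 and 0.00114, which distinguish the two cases.

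**7. Log scale.** 1 ng/mL = 1 ug/L, so the reported Cmax is 32,200 ug/L. 32,200/10^4 = 3.2, and log10(32,200) = 4.51 against a highest listed exponent of 4. One more decade covers it: 10^5/32,200 = 3.1.

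**The case against.** The strongest reply is that almost nothing is lost. The Table 4 column is headed as display digits, so it governs printing and not computation. t½ sits in the next row at 3 significant figures, and λz can be recovered from it: 25.4 days prints as 610 h, and 0.6931/610 = 0.00114. No hypothesis is tested. SAP 8.5.1 may also add digits to the summaries. All of this stands and limits the point to presentation. It does not defend the cell, because a parameter listed as primary should be readable in its own column. The possible extra digits depend on how SAP 8.5.1 is read for a derived quantity. That section also sets no digits for the confidence limits of the geometric mean, but this gap affects every PK parameter and is not specific to λz.

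A reader might infer that rounding λz to 0.00 damages AUCinf, CL, Vss or the reliability criteria. The documents do not support this: nothing in the SAP feeds the displayed value back into any derivation.

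On the plots, a reader might infer that the peak will be cut off. The SAP does not call the listed powers axis limits. Its only removal rule for the log plots concerns values at the LLOQ, and if the list is just a set of tick values, nothing is lost. Nor can one reliably predict from the protocol's compartmental values how many samples would exceed 10^4. The protocol gives volumes and clearance in absolute terms in one section and per kg in another, with no stated relation to body weight. The direct comparison of 32,200 with 10^4 is all the documents support, and it is enough.

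**Conclusion.** The λz format in SAP Table 4 is wrong as written. At the protocol's half-lives, λz is 0.00131 or 0.00114 per hour, and individual values print as 0.00. The half-life would have to be about a quarter of the expected one, 5.8 days or less, before 0.01 appeared. The conclusion assumes that half-lives in Japanese volunteers are broadly like those in the earlier study, and it has a margin of about fourfold. The effect is minor: it is a display error, no estimate is biased, and t½ preserves the information.

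The log-scale list is a mismatch with the reported Cmax at the same dose (a factor of 3.2). Loss of the peak from the log figures is conditional on the list being used as axis limits. Even then, the tabulated Cmax and CEOI, the concentration listing and the linear plots would keep the data.

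**What to change.** In SAP Table 4, change the λz display to 3 significant figures, and state that the same precision applies to its summary statistics, including the confidence limits of the geometric mean. This matches t½, CL, Vss and MRT in the same table.

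In SAP 14.1.2 and 14.1.3, extend the listed log-scale values to 10^5 ug/L.

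The cost is one table cell with a short note, and one line in each of two figure specifications. No new data, analysis or change to any derivation is needed.
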